Improving Vision in Adults With Macular Degeneration, Study 1: the Effect of Brain Stimulation

Study Protocol Outline

Date Approved by Researchers: September 19, 2019

Inclusion Criteria

- Diagnosis of AMD (age 60+) or JMD (current age 18+).
- Central vision loss and use of a PRL (confirmed by a microperimeter).
- Visual acuity (VA); between 0.5 and 1.0 logMAR inclusive (6/18-6/60) in the better eye.
- Best-corrected near visual acuity of 4.0M at 40 cm or better in the better eye
- Stable vision for the previous 3 months (by patient report).

Exclusion Criteria

- Diagnosed dementia.
- Not fluent in reading English (Waterloo) or Chinese characters (Hong Kong).
- any ocular surgery (including anti-vegF injections) within the duration of the study.
- Ocular pathology other than JMD or AMD that can reduce central vision.
- Severe hearing impairment.

Contraindications for tDCs:

- Suffer from epilepsy, have had an epileptic seizure, or family history of epilepsy.
- Any metal implant (excluding tooth fillings).
- Implanted medication pump or implanted electronic device, including pacemaker or defibrillator
- Heat disease, neurological condition, or have had neurological or cardiac surgery.
- Recurring headaches
- Skull fracture or head injury
- Head or Brain surgery
- Pregnancy
- Skin Condition
- Taking any medication on the list on Form A
- Excessive alcohol (>2 standard drinks) or slept dramatically less the usual in the last 24 hours.

Protocol Outline

Day 0: Pre-Screening

1. Potential participants are recruited
 - Done by clinician for privacy and also to make an initial assessment about eligibility.
 - Diagnosis of AMD or JMD with VA in the inclusion range
 - Age ≥ 18
 - No diagnosis of dementia
 - No other eye disease or condition affecting vision
 - No indication of being not fluent reader in tested language
2. Call potential participants to recruit.

Day 1: Screening and RSVP baseline selection

1. Consent form and signature
2. Refraction
3. Distance ETDRS acuity.
4. Near VA (MNREAD with stopwatch) and with +4D in trial frame).
5. Decide on eye to be used (eye with better near reading vision)
6. Ocular health check (of the eye to be used)
7. PRL measure with microperimetry
8. If better eye has another ocular disease or not a stable PRL, check the poorer eye for eligibility and use that for all further testing

If patient qualifies for main study:

10. Full RSVP test [45+ minutes]

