 - 5 print sizes by 5 reading speeds, selected based on the MNREAD test results.
11. Select single print size and word speed combination that is predicted to elicit 55% with the following procedure:
 - Fit a two-line function and a simple linear regression to the data
 - i. If two-line fit is better (a CPS/ “elbow” was found):
The CPS defines the print size and word speed to be used
 - ii. If simple linear regression is better (no reliable “elbow” found):
Use print size of 1.5 deg x-height and corresponding reading speed
12. Blind-selection of stimulation codes to determine active/sham schedule for participant
 - Active/sham stratified by:
 - i. VA – [0.5, 0.8) and [0.8, 1.0] logMAR groups, to be balanced as far as stimulation schedule

NOTE: JMD participants will not be stratified by VA, but active/sham schedules will be balanced for JMD participants.

Treatment Days: *(treatment days must be separated by 2 – 14 days, otherwise redo baseline measures.)*

- Order of crowded and uncrowded tests is randomized on a per-subject basis but maintained throughout testing for each patient.
 - Setup consists of two computers. One computer 3 meters away for the crowded and uncrowded Landolt C test, and one computer on an independently rolling cart. The RSVP task will be done on the rolling computer, and then will be moved out of the way for the participant to do the Landolt C tests. This allows older patients to not be required to move continuously for these tests.
1. Primary outcomes pre-test.
 - a. specifically-selected RSVP condition tested.
 2. Secondary outcomes pre-test. Computer is fixed 3 meters away.
 - a. Crowded Landolt C
 - b. Uncrowded Landolt C
 - c. Manually calculate measure of crowding strength:
 3. Stimulation (either active or sham) for 20 minutes.
 - a. During stimulation: specifically-selected RSVP condition tested
 - b. During stimulation: Crowded and Uncrowded Landolt C
 4. Five minutes after stimulation end:
 - a. Specifically-selected RSVP condition tested
 - b. Crowded and Uncrowded Landolt C tested
 5. Thirty minutes after stimulation end:
 - a. Specifically-selected RSVP condition tested
 - b. Crowded and Uncrowded Landolt C tested

6. Participant fills out a brain stimulation adverse-effects questionnaire.
7. ONE THE FINAL TREATMENT DAY: administer blind MoCA cognitive test for use in sensitivity analysis/as a covariate

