8. After sending patient home, use custom-written program to process all patient data collected for that day for the individual subject.

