NCT04111068

Official Title: Improving Vision in Adults With Macular Degeneration, Study 1: the Effect of Brain Stimulation

Date Last Updated: February 4, 2022

Statistics Analysis Plan

Planned Study Components

- A. Independent Variables:
 - 1. Stimulation Type (active vs sham)
 - 2. Test Time (effect during, effect 5 mins post, effect 30 mins post)
 - For statistical testing, Test time will contain 3 levels, defined as:
 - i. During stimulation baseline
 - ii. 5 mins post stimulation baseline
 - iii. 30 mins post stimulation baseline
- B. Experimental Design and Outcome Measures:
 - 1. 2 (Stim type) x 3 (Test time) analysis: Outcome is Crowded VA in logMAR (FrACT)
 - 2. 2 (Stim type) x 3 (Test time) analysis: Outcome is Uncrowded VA in logMAR (FrACT)
 - 3. 2 (Stim type) x 3 (Test time) analysis: Outcome is RSVP reading analysis
- C. *Interactions:* An interaction between stim type and test time indicates that active stimulation was effective, but not at every timepoint. Therefore, the planned contrast in the event of an interaction:
 - 1. Active vs. sham: individually compare active vs sham at the three timepoints.
- D. Covariates to examine:
 - 1. Language, primary analysis (dichotomous)
 - 2. Age (continuous)
 - 3. Distance visual acuity (will be dichotomized)^a
 - 4. RSVP critical print size (will be dichotomized)^a
 - 5. RSVP maximum reading speed (will be dichotomized) ^a
 - 6. Cognitive Screening: MoCA-blind (UW) and (HKPU) (will be dichotomized) ^b
 - 7. Type of AMD: wet, dry (dichotomous) ^c
 - a. Because the different languages likely elicit different mean performances, covariates listed will be dichotomized with a median split separately for each language to allow combined data analysis with the included covariate. The "low" group will include any participants scoring the median. The "high" group will include only participants scoring better than the median.
 - b. Cognitive Screening will be dichotomized separately for each language along standard thresholds for clinical significance. This covariate will only be tested if at least 5 total participants are allocated to both groups.
 - c. Type of AMD will only be tested if at least 5 total participants are allocated both groups.
- E. Additional Details:
 - 1. The analysis will be run individually for each planned outcome measure.
 - 2. Participants with incomplete data will be excluded from the analysis
 - 3. All tests will be 2-tailed with alpha = 0.05

Analysis Procedure

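### The blind MoCA is given only after stimulation on the final treatment day, yet the SAP uses it as a dichotomised covariate that can define subgroups

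*Protocol*

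**What the plan says.** In the Protocol, Treatment Days, the numbered steps of a session are:

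- Steps 1 and 2: pre-tests (RSVP, then crowded and uncrowded Landolt C).
- Step 3: "Stimulation (either active or sham) for 20 minutes", with RSVP and Landolt C tested while it runs.
- Step 4: the same tests five minutes after stimulation ends.
- Step 5: the same tests again, "Thirty minutes after stimulation end".
- Step 6: "Participant fills out a brain stimulation adverse-effects questionnaire".
- Step 7, on the final treatment day only: "administer blind MoCA cognitive test for use in sensitivity analysis/as a covariate".
- Step 8: "After sending patient home, use custom-written program to process all patient data collected for that day".

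The list headed "Day 1: Screening and RSVP baseline selection" covers refraction, acuity, MNREAD, microperimetry and the full RSVP test. It contains no cognitive test. Day 0 and the exclusion criteria screen only for diagnosed dementia.

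The SAP, section D, item 6, lists "Cognitive Screening: MoCA-blind (UW) and (HKPU) (will be dichotomized". Note b sets the cut at standard clinical thresholds, separately by language and without a numeric value, and requires at least 5 participants in each group before the covariate is tested. Under section 2a, Secondary Analysis, a dichotomous covariate that is significant, or that interacts significantly with another factor, leads to a separate repeated-measures ANOVA for each of its levels. Section 2b applies the nonparametric primary procedure to each covariate in the same way.

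**The concern.** A variable used to sort participants into subgroups is best fixed before the treatment under study can touch it. Here the score is taken at the end of the last session, so two influences could enter it.

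- **Fatigue.** If the session lowers scores generally, some participants near the threshold fall into the low group who would not have done so when fresh. With a minimum of 5 per group, a few such moves could decide whether the covariate is tested at all.
- **The last stimulation given.** Some participants have active stimulation on the final day and others sham. If stimulation shifts the score, MoCA group becomes associated with the order of active and sham. The SAP's models have no period or sequence term, so a period effect in the outcome could then look like a difference between MoCA groups in the response to stimulation.

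At stake is how the MoCA analysis can be read, not the primary analysis, which uses language as its only covariate.

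**Working it through.** Neither document states a figure on this point, so there is nothing to reproduce. The check has three parts.

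**1. Order of events.** Step 8 begins once the patient has gone home, which supports reading the steps in time order. MoCA is then the last procedure with the participant. From the start of stimulation to the start of the last test round is at least 20 + 30 = 50 minutes. The pre-tests come before that, and the last round and the questionnaire after it. Four test rounds precede MoCA: before, during, 5 minutes after and 30 minutes after stimulation.

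Among the seven covariates in SAP section D, a session cannot change language, age or AMD type. Distance acuity, RSVP critical print size and RSVP maximum speed are measured on Day 1. MoCA is the only one collected solely after stimulation.

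**2. Illustration of fatigue.** Assumptions, none from the documents: scores are normal, the cut-off lies c SD from the unshifted mean, and everyone's score falls by s SD. The share moved into the low group is Φ(c + s) − Φ(c).

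| c | s = 0.1 | s = 0.25 | s = 0.5 |
|---|---|---|---|
| −1 | 0.1841 − 0.1587 = 2.5% | 0.2266 − 0.1587 = 6.8% | 0.3085 − 0.1587 = 15.0% |
| −0.5 | 0.3446 − 0.3085 = 3.6% | 0.4013 − 0.3085 = 9.3% | 0.5000 − 0.3085 = 19.1% |
| 0 | 0.5398 − 0.5000 = 4.0% | 0.5987 − 0.5000 = 9.9% | 0.6915 − 0.5000 = 19.1% |

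The range over the grid is roughly 3% to 19%. Between grid points the largest value for s = 0.5 is at c = −0.25: 0.5987 − 0.4013 = 19.7%. The documents give no sample size. In an assumed sample of 20, the range is 20 × 0.025 = 0.5 to 20 × 0.191 = 3.8 people.

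**3. Illustration of session order.** Further assumptions: two treatment days, equal numbers in each order, a median cut-off, and scores d SD higher after an active final day than after a sham one. The share of the high group with active last is Φ(d/2), and of the low group 1 − Φ(d/2). The bias in a subgroup's active-minus-sham difference is the period effect × (2 × share − 1). The bias in the high-minus-low difference is therefore the period effect × 2 × (high share − low share).

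| d | High group, active last | Low group, active last | Bias, as a multiple of the period effect |
|---|---|---|---|
| 0 | 0.500 | 0.500 | 0 |
| 0.1 | 0.520 | 0.480 | 0.080 |
| 0.2 | 0.540 | 0.460 | 0.159 |
| 0.3 | 0.560 | 0.440 | 0.238 |
| 0.5 | 0.599 | 0.401 | 0.395 |

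(The last column uses unrounded shares.) The period effect is unknown, so these are multipliers and not estimates of bias. A score taken before any stimulation has d = 0 by design, which is the first row.

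**The case against.** The case for leaving the test where it is has several parts.

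- **The comparison is within-person.** A participant who completes the schedule should have had both active and sham by the time of MoCA. A reader might infer that the score is contaminated by treatment arm, as in a parallel-group trial. The design does not support that. This stands.
- **The order mechanism needs a chain of conditions.** Stimulation must shift MoCA, the shift must last past the 30-minute tests, and the outcome must have a period effect. The documents establish none of these. Each treatment day has its own pre-test, and the SAP words test time as effects relative to baseline, so plain drift between days should largely drop out. Schedules are also balanced within acuity groups and among JMD participants. This stands as a limit on size. It does not make the score independent of order.
- **Fatigue is assumed.** Treatment days test one selected RSVP condition, with a gap between the 5-minute and 30-minute rounds. At a shift of 0.1 SD fewer than one person in 20 changes group. This stands.
- **Early leavers.** A reader might infer that people who stop before the last day distort the analysis because they have no score. SAP section E, item 2, already excludes participants with incomplete data, so the placement of MoCA changes little for them.
- **Testing last protects the outcomes.** With MoCA at the end, its burden falls on no efficacy measurement. That is a reasonable trade-off, though the documents do not give it as a reason. It rules out giving MoCA before the pre-test on the first treatment day, where it would burden the primary outcome on one treatment day only. It does not rule out Day 1.

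**Conclusion.** The timing is as described, and MoCA is the one SAP covariate measured solely after stimulation. Because it is dichotomised, subject to a minimum count and able to trigger separate ANOVAs, its value should not be open to influence from the session or from stimulation order. This is a minor point. It touches a secondary covariate that is analysed only if both groups reach 5, and it leaves the primary analysis alone.

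The 3% to 19% range rests wholly on assumed shifts and cut-offs. The 0.080 to 0.395 multipliers add an assumed number of treatment days, an assumed stimulation effect on MoCA and an unknown period effect. A reader might take these figures as evidence that the MoCA subgroups are biased. They show only what could follow if the assumptions held.

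**What to change.** Move the blind MoCA to Day 1, before any stimulation. Give it once eligibility is confirmed, so that people who do not qualify are spared it, and preferably after the full RSVP test (step 10), so that it cannot affect the choice of print size and word speed. Do not place it before the pre-test on a treatment day.

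The cost is a change of Protocol wording and a slightly longer Day 1; no procedure is added. Some fatigue from Day 1 testing may remain in the score, since the RSVP test alone takes 45 minutes or more, but it cannot depend on stimulation or session order.

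If the data are already collected, tabulate MoCA by stimulation order (active last or sham last), state when the test was given, and label the MoCA subgroup results exploratory. This needs only one table and a sentence in the report.

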NCT04111068

Official Title: Improving Vision in Adults With Macular Degeneration, Study 1: the Effect of Brain Stimulation

Date Last Updated: February 4, 2022

Statistics Analysis Plan

Planned Study Components

- A. Independent Variables:
 - 1. Stimulation Type (active vs sham)
 - 2. Test Time (effect during, effect 5 mins post, effect 30 mins post)
 - For statistical testing, Test time will contain 3 levels, defined as:
 - i. During stimulation baseline
 - ii. 5 mins post stimulation baseline
 - iii. 30 mins post stimulation baseline
- B. Experimental Design and Outcome Measures:
 - 1. 2 (Stim type) x 3 (Test time) analysis: Outcome is Crowded VA in logMAR (FrACT)
 - 2. 2 (Stim type) x 3 (Test time) analysis: Outcome is Uncrowded VA in logMAR (FrACT)
 - 3. 2 (Stim type) x 3 (Test time) analysis: Outcome is RSVP reading analysis
- C. *Interactions:* An interaction between stim type and test time indicates that active stimulation was effective, but not at every timepoint. Therefore, the planned contrast in the event of an interaction:
 - 1. Active vs. sham: individually compare active vs sham at the three timepoints.
- D. Covariates to examine:
 - 1. Language, primary analysis (dichotomous)
 - 2. Age (continuous)
 - 3. Distance visual acuity (will be dichotomized)^a
 - 4. RSVP critical print size (will be dichotomized)^a
 - 5. RSVP maximum reading speed (will be dichotomized) ^a
 - 6. Cognitive Screening: MoCA-blind (UW) and (HKPU) (will be dichotomized) ^b
 - 7. Type of AMD: wet, dry (dichotomous) ^c
 - a. Because the different languages likely elicit different mean performances, covariates listed will be dichotomized with a median split separately for each language to allow combined data analysis with the included covariate. The "low" group will include any participants scoring the median. The "high" group will include only participants scoring better than the median.
 - b. Cognitive Screening will be dichotomized separately for each language along standard thresholds for clinical significance. This covariate will only be tested if at least 5 total participants are allocated to both groups.
 - c. Type of AMD will only be tested if at least 5 total participants are allocated both groups.
- E. Additional Details:
 - 1. The analysis will be run individually for each planned outcome measure.
 - 2. Participants with incomplete data will be excluded from the analysis
 - 3. All tests will be 2-tailed with alpha = 0.05

Analysis Procedure

- 1. Normality check: Check if ANOVA assumptions are violated (languages combined)
 - 1. Sphericity of variances use Mauchly's Test of Sphericity to check for significant violations of sphericity.
 - Normality of Residuals visually inspect pp plot and qq residual plots evaluate the degree of violation.
 - If sphericity assumption is violated: Use Greenhouse Giesser correction for all main effects and interactions, following *Parametric Statistics*, section 2a
 - If interaction between independent variables is significant: Use Wilcoxonsigned-rank tests for planned pairwise comparisons instead of ttests.
 - If normality assumption is violated: follow *Nonparametric Statistics*, section 2b.

2a. Parametric Statistics

- 1. Primary Analysis:
 - i. Perform repeated-measures ANCOVA, with Language as covariate.
 - If interaction between stimulation type and test time is significant:
 - ii. Examine planned comparisons with within-subject ttests

If language covariate is significant or significantly interacts with another factor:

iii. Run separate repeated-measures ANOVAs for each language

If either ANOVA reveals an interaction:

- iv. Examine planned pairwise comparisons with within-subject ttests
- 2. Secondary Analysis:
 - i. Perform repeated-measures ANCOVA, iteratively with each secondary covariate to be tested.

If interaction between stimulation type and test time is significant:

ii. Examine planned comparisons with within-subject ttests

If any dichotomous covariate is significant or significantly interacts with another factor: iii. Run separate repeated-measures ANOVAs for each level of the covariate

If either ANOVA reveals an interaction:

iv. Examine planned pairwise comparisons with within-subject ttests

2b. Nonparametric Statistics

- 1. Primary Analysis:
 - i. Perform aligned rank transform for nonparametric ANOVA with 3 independent factors.
 - 2 (Stim type) x 3 (test time) x 2 (language) mixed effects ANOVA

If stim type and test time interact, but language is not significant and no interaction involving language occurs:

ii. Run planned pairwise comparisons using Wilcoxon-signed-rank tests

If language is significant or if language significantly interacts with any other factor:

iii. Discard previous analysis and run two separate ART-transformed 2 (stim type) x 3 (test time) nonparametric ANOVAs, one for each level of language.

If either ANOVA reveals an interaction:

iv. Run planned pairwise comparisons with Wilcoxon-signed-rank tests

2. Secondary Analysis:

i. Perform the same procedure as the primary analysis iteratively for each covariate to be tested.

Aligned-rank transform reference:

Wobbrock et al. (2011). The aligned rank transform for nonparametric factorial analyses using only ANOVA procedures. Proceedings of the SIGCHI conference on human factors in computing systems. https://dl.acm.org/doi/10.1145/1978942.1978963

Data and demographics summary table:

- 1. A summary table will be generated, one row per participant. Columns will include:
 - Age
 - Sex
 - macular degeneration type (wet AMD, dry AMD, JMD
 - language
 - distance VA
 - MNREAD CPS (equivalent to near VA)
 - MNREAD speed
 - RSVP CPS
 - RSVP speed

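### The full-set stimulation main effect is built on change scores without adjustment for the same-day pre-test or session order: valid, but less precise than it need be over most of the assumed range

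*SAP*

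**What the plan says.** The Protocol (Treatment Days, steps 1 to 5) has each outcome tested before stimulation, during it, and 5 and 30 minutes after it. SAP section A.2 names the factor as "Test Time (effect during, effect 5 mins post, effect 30 mins post" and then says "For statistical testing, Test time will contain 3 levels, defined as", listing three levels that each refer to baseline. The pre-test is not a level.

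The primary parametric model (2a.1.i) is: "Perform repeated-measures ANCOVA, with Language as covariate". The rank-based model (2b.1.i) has stimulation type, test time and language. The secondary covariates in section D are age, distance acuity, RSVP critical print size, RSVP maximum speed, cognitive screening and AMD type. All are participant-level. None is the treatment-day pre-test, and no model has a session-order term.

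Single-time contrasts (section C: "Active vs. sham: individually compare active vs sham at the three timepoints") are run only under the condition "If interaction between stimulation type and test time is significant".

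The Protocol (Day 1, step 12) balances active/sham schedules within two acuity bands cut at 0.8 logMAR, and separately for JMD participants.

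**The concern.** Section C treats an interaction as the sign that stimulation worked at some times but not all. A benefit of equal size at all three times produces no interaction, so it can be detected only through the stimulation main effect. That is the test in which the pre-test's noise matters most. Averaging the three later scores reduces their noise, but the same single pre-test is subtracted from each, so its noise does not average out. Participant-level covariates cannot remove it, because they do not vary between the active and sham sessions. What is at stake is power for the main effect, using a measurement that the trial already takes.

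**Working it through.** **Inputs from the documents.** Three later tests and one pre-test per treatment day (Protocol, Treatment Days); paired active-sham comparisons (SAP 2a); two-sided alpha 0.05 (SAP E.3). The documents give no sample size, power, SD or correlation, so there is no planned figure to reproduce.

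**Assumptions.** One active and one sham session per participant, with an even split of schedules. Within-participant variance is 1 per test, of which a share L is stable within a session and 1−L is test noise, equal at all four tests and equally correlated over time. L is unknown, so a range is shown. Language is left out of the arithmetic.

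**Main effect (mean of three later scores), variance per session.**
- Change score: (1−L)/3 + (1−L) = 4(1−L)/3.
- Adjusted for the pre-test: [L + (1−L)/3] − L² = (1−L)(1+3L)/3.
- Ratio, large sample: 4/(1+3L).

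**Single timepoint.** Change 2(1−L); adjusted 1−L²; ratio 2/(1+L).

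**Finite samples.** Estimating the pre-test slope alongside the intercept and schedule multiplies either ratio by (n−4)/(n−3): 0.857, 0.941 and 0.963 at n = 10, 20 and 30.

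Example, n = 20 and L = 0.5: 0.667/0.417 = 1.60, and 1.60 × 16/17 = 1.51.

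| Change score over adjusted | L=0.25 | L=0.5 | L=0.75 | L=0.9 |
|---|---|---|---|---|
| Main effect, n=10 | 1.96 | 1.37 | 1.05 | 0.93 |
| Main effect, n=20 | 2.15 | 1.51 | 1.16 | 1.02 |
| Main effect, n=30 | 2.20 | 1.54 | 1.19 | 1.04 |
| Single time, n=20 | 1.51 | 1.25 | 1.08 | 0.99 |

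Simulation at n = 20 gave main-effect ratios of about 2.17, 1.51, 1.14 and 1.04. Where the change-score main effect has power 0.60 at n = 20, simulated adjusted power is 0.898, 0.770, 0.660 and 0.605 across the four values of L. Null rejection was 0.049 to 0.051.

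**Break-even.** Setting the ratio to 1 gives L = (3n−13)/(3(n−3)) for the main effect: 17/21 = 0.81, 47/51 = 0.92 and 77/81 = 0.95 at n = 10, 20 and 30. For a single time, L = (n−5)/(n−3): 0.71, 0.88 and 0.93.

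**Stimulation by time.** This test uses differences between times within a session, so the pre-test cancels exactly: ratio 1.00.

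**Session order.** A shift in level between sessions cancels in change scores. If instead the within-session gain differs between sessions by g (in SDs of the paired difference), a 10/10 split has no bias, but without a session term power falls from 0.60 to 0.57 (g = 0.25) or 0.51 (g = 0.5). The two terms belong together: with a level shift of 0.5 and L = 0.5, adjusting for the pre-test alone gave a bias of 0.045 at a 12/8 split and 0.066 at 13/7, against 0.00 with both terms.

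**Error structure.** Regression of paired differences held about 5% false positives. The same terms fitted with participant effects only gave about 11% (L = 0.25), 16–17% (0.5), 19–20% (0.75) and 21–22% (0.9) for the main effect.

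**The case against.** The strongest reply is that nothing in the plan is invalid. That stands: change scores hold about 5% error, and the interaction test that gates the planned contrasts is untouched. It is also true that the size of the gain comes from a model and not from a figure in the documents, and that its sign reverses at high L or in small sets. This limits the point to a modest precision gain.

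Three stronger readings are tempting and are not supported.

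- *Baseline is undefined.* The lines defining the levels appear to have lost a symbol in extraction, which is not a fault of the plan. No Landolt C test is listed on Day 1, so for the two acuity outcomes baseline can only be the treatment-day pre-test. For RSVP, the Protocol also uses the word for Day 1 measures, so a clarifying sentence would help, but that is missing detail. If raw scores were meant, the pre-test would go unused, and in large samples adjustment would still gain whenever L is above 0.
- *Subset analyses are biased.* The SAP does provide for subsets ("Run separate repeated-measures ANOVAs for each language", and splits by covariate level), and schedule balance is not stated for most of them. An uneven split n1/n2 gives a bias of g(n1−n2)/n, but only if the gain differs between sessions. Averaged over random schedules the bias is 0, and rejection at g = 0.5 is 0.045 (n = 5) and 0.040 (n = 10). Even given 7/3 or 4/1 splits it is only 0.060 or 0.065.
- *Adjust everywhere.* In a 4/1 subset with g = 0, the session term cuts power from 0.60 to 0.37. In the rank-based setting, subtracting fitted terms before a signed-rank test raised false positives from 0.048–0.051 to 0.069–0.083.

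**Conclusion.** The point holds as one of precision for the full-set parametric analysis. The planned analysis is valid, but the stimulation main effect is less precise than it could be over most of the assumed range: by a factor of about 1.5 in variance at n = 20 if half the within-participant variance is stable within a session, and by almost nothing at L = 0.9. Above L of about 0.81, 0.92 or 0.95 (n = 10, 20, 30) adjustment no longer pays. The loss is smaller for single-time contrasts and nil for stimulation by time. These sizes rest on assumed n, L, two sessions, and equal noise and correlation over time. A reader might infer bias or inflated error; the documents do not support that. Severity is minor: a cheap improvement.

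**What to change.** For the full-set parametric analysis only:

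- Test the stimulation main effect by regressing each participant's active-minus-sham difference in the mean of the three later scores on the active-minus-sham pre-test difference and the schedule (+1/−1 for order of sessions), with language kept as planned. Leave the pre-test difference uncentred, so that the intercept is the stimulation effect at equal pre-tests.
- Equivalently, fit a mixed model with these terms and an explicit session-within-participant random effect or error stratum. Do not fit them with participant effects only.
- Where the parametric single-time contrasts use paired t-tests, use the same regression of paired differences.
- State in one sentence that baseline means the same-day pre-test, if that is intended.

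Leave the stimulation-by-time test, the Wilcoxon comparisons, the rank-based branch and the small language or covariate subsets as planned. Report the schedule split for every analysed set.

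Cost: two error degrees of freedom, no new data, and a slight loss of precision if L is about 0.9 or above or the set is very small.

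### SAP section C reads a stimulation-by-time interaction as proof of efficacy, but that test has no direction

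*SAP*

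**What the plan says.** SAP section C (Interactions) gives the rule of interpretation: "An interaction between stim type and test time indicates that active stimulation was effective, but not at every timepoint". It goes on: "Therefore, the planned contrast in the event of an interaction", and names active versus sham at each of the three test times.

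The Analysis Procedure makes the interaction the gate to those contrasts. In 2a (parametric) the condition is "If interaction between stimulation type and test time is significant" and the step is "Examine planned comparisons with within-subject ttests". In 2b (nonparametric) the step after an interaction, when language plays no part, is "Run planned pairwise comparisons using Wilcoxon-signed-rank tests". Section E.3 makes every test two-sided at 0.05.

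On outcomes, section B lists crowded acuity, uncrowded acuity and, third, "2 (Stim type) x 3 (Test time) analysis: Outcome is RSVP reading analysis", with no ranking. Section E.1 adds: "The analysis will be run individually for each planned outcome measure". In the SAP the word primary marks the model with language as covariate, not an outcome. The protocol does rank outcomes: under Treatment Days, step 1 places RSVP under a primary heading and step 2 places the Landolt C tests under a secondary one.

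**The concern.** Section C attaches a conclusion about efficacy to a test that cannot tell benefit from harm. Both halves of the sentence fail. Efficacy does not follow, because worsening at one time also makes the active-sham difference vary. Absence of effect at some time does not follow either, because benefit at all three times that differs in size makes the difference vary too.

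The contrasts come next, but section C introduces them as a consequence of the efficacy statement, not as a condition for it. Nothing in the SAP says which governs if the interaction is significant and no contrast favours active, or if all three do. At stake is the wording of the conclusion: the plan supplies a sentence that its own next step could contradict.

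**Working it through.** **Inputs from the documents.** Two stimulation types, three test times, within-subject comparison, two-sided 0.05 for each test, contrasts run after a significant interaction. The SAP gives no sample size, SD, effect size or correlation, so there is no planned figure to reproduce.

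**Step 1: the test has no sign (no assumptions needed).** Let d_j be the mean active-minus-sham difference at time j, scaled so that positive favours active, and let d be the average of the three. In the two-by-three within-subject analysis,

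F = [n Σ(d_j − d)² / 2] / [SSE / (2(n − 1))].

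Reversing the sign of every difference leaves F unchanged. So does adding a constant to all three. With true differences in SD units, Σ(d_j − d)² is:

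| Pattern | Average | Sum of squares |
|---|---|---|
| Harm at one time: 0, 0, −0.8 | −0.267 | 0.267² + 0.267² + 0.533² = 0.427 |
| Benefit at one time: 0, 0, +0.8 | +0.267 | 0.427 |
| Unequal benefit at all times: 1.2, 0.8, 0.4 | 0.8 | 0.4² + 0² + 0.4² = 0.32 |
| Equal benefit at all times: 0.6, 0.6, 0.6 | 0.6 | 0 |

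The first two rows are indistinguishable to the interaction test. The third gives an interaction although active is better throughout. The fourth gives one only at the 5% error rate.

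**Step 2: how often this would show (assumed values).** Take n = 20, SD of the paired difference 1, and correlation r between the differences at the three times. The noncentrality is n Σ(d_j − d)² / (1 − r), and the critical value of F(2, 38) is 3.245. For harm at one time with r = 0.5: 20 × 0.427 / 0.5 = 17.1, which gives power of about 95%. For unequal benefit: 20 × 0.32 / 0.5 = 12.8, which gives about 88%. Simulation (40,000 trials per setting) gives:

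| | r = 0 | r = 0.3 | r = 0.5 | r = 0.7 |
|---|---|---|---|---|
| Harm at one time: interaction significant | 0.708 | 0.862 | 0.952 | 0.997 |
| Of those: no contrast favours active | 0.932 | 0.945 | 0.951 | 0.959 |
| Of those: a contrast significantly against active | 0.988 | 0.959 | 0.939 | 0.926 |
| Unequal benefit: interaction significant | 0.578 | 0.742 | 0.879 | 0.983 |
| Of those: all three contrasts significantly favour active | 0.212 | 0.297 | 0.350 | 0.389 |

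The right-hand columns fit the design better. Each treatment day has one pre-test. If test time is analysed as change from that pre-test, as SAP A.2 appears to intend, the three changes share it, and independent errors of equal variance give r = 0.5. Adding language as a two-level factor (10 per group) moves the interaction rates, and the share with no favourable contrast, by less than 0.01.

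**Step 3: error rate on a single outcome.** With no true effect, count as a favourable result either a main effect favouring active or an interaction followed by a contrast favouring active. The rate is 0.035 at r = 0.5 and 0.032 at r = 0.7, against 0.025 for one two-sided test.

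**Step 4: adjusting the contrasts.** For benefit of 0.8 SD at one time, power for that contrast after the gate is 0.895 (r = 0.5) and 0.924 (r = 0.7). With Holm it is 0.800 and 0.821, a loss of 0.095 and 0.103. Favourable false claims at the other two times, given a significant interaction, fall from about 4% to about 2%.

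**The case against.** The strongest reply is that the sentence is only the rationale for a procedure. It leads directly to active-versus-sham contrasts at all three times, sections 2a and 2b repeat that step, and every test is two-sided, so harm would appear as harm. To report efficacy against the contrasts, an analyst would have to ignore the SAP's next instruction. This stands as a limit. A reader might infer that the trial will claim benefit from the interaction alone, even when active is worse. No passage says so, and the harm simulation illustrates the missing sign rather than measuring a risk to this trial. It does not rescue the sentence, which states a false inference and is not made conditional on any contrast.

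A reader might also infer that the trial has no primary outcome and that a finding on any of three outcomes would count. If they were unranked, the chance of a favourable false result on at least one would be 6% to 13% under the simulated settings. The protocol's headings put RSVP first, and the SAP does not contradict them. The gap is that the SAP does not repeat the ranking.

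Finally, the lack of a follow-up step for the main effect is not in itself a defect. A two-level factor needs no further contrast, and section C implies the usual factorial reading. It leaves that reading unstated, so a line of clarification is reasonable.

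**Conclusion.** The section C sentence is wrong as written and should be replaced. That rests on the algebra of the F statistic and holds for any sample size, SD or correlation. The percentages are illustrations at an assumed n of 20.

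The rest is smaller. The ranking of outcomes and the reading of a main effect are clarifications. A reader might take the roughly 10% chance of a significant main effect or interaction on one outcome, with no true effect, as serious inflation. That figure counts both directions. In favour of active it is about 3% to 3.5% against 2.5% (n = 20, r = 0.5 to 0.7), which is small. The documents therefore do not support treating the three unadjusted contrasts as an error that must be corrected.

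**What to change.** Replace the sentence in section C with:

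> An interaction indicates that the active-sham difference varies with test time; after an interaction, benefit is claimed only at timepoints where the active-vs-sham contrast significantly favours active.

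This changes wording only, with no new data or test. It does make a claim harder to reach. For a true benefit of 0.8 SD at one time (n = 20, r = 0.5 to 0.7), the interaction is significant in 0.952 to 0.997 of trials and the contrast at that time is also significantly favourable in 0.895 to 0.924. About 6 to 7 trials in 100 would therefore have an interaction without support at that time.

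In the same amendment:

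- State in section B that RSVP is primary and crowded and uncrowded Landolt C acuity are secondary, as in the protocol. Acuity results then become supportive.
- State how a stimulation main effect without an interaction is read.

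Adjusting the three contrasts, for example by Holm, is the sponsor's choice. It costs about 10 points of power for a one-time effect under these assumptions. If adopted, section E.3 must say so.
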